Parkinson's Disease Questionnaire-39 Scale	X p									X
Parkinson's Disease Sleep Scale-2	X p									X
Columbia-Suicide Severity Rating Scale	X p						X	X		X
EuroQol-5 Dimensions-5 Levels Survey	X p									X
Clinical Global Impression-Severity	X p									X
Clinical Global Impression-Improvement										X
Randomization	X q									
Surgery and related procedures			X							
Stereotactic imaging following frame placement (CT or MRI)			X							
Limited-cut CT at catheter tip to confirm localization following infusion (AAV-GAD groups only)			X							
Non-contrast CT of head within 24 hours after catheter removal (AAV-GAD groups only)				X						
Sham limited-cut CT at catheter tip to confirm localization following infusion (SHAM group only)			X							
Sham non-contrast CT of head within 24 hours after catheter removal (SHAM group only)				X						
Study drug administration			X							
Removal of catheter			X							
Removal of sutures and burr hole site assessment						X				
Anti-GAD and anti-AAV2 antibody evaluation (humoral immune response)		X					X	X		X

Study Day/Month	Screening		Surgery/ Hospital		UV	Day 15 ±2 days	Day 29 ±3 days	Week 12 ±7 days	Week 19 a ±7 days	Week 26/EW ±7 days
	Day -40 to Day -8	Day -7 to Day -3	Day 1	Day 2						
Hauser Patient Diary review		X				X r		X r		X r
Check on control of Parkinsonism, and other neurological events									X	

Note: If, despite all efforts to encourage the participant to continue in the study, the participant withdraws consent after Day 1, every effort should be made to complete the full panel of assessments scheduled for the Week 26 visit.

During visits that include the MDS-UPDRS assessment, the MDS-UPDRS Part 3 “off” state assessment should preferably be performed before any other assessments or questionnaires.

- a. Telephone visit. Participants will be contacted by telephone for assessment of AEs, changes in control of Parkinsonism, and other neurological events.
- b. Assessments preferably to be performed between Day -40 and Day -21.
- c. MRI and FDG-PET scans done for surgical screening will be used as baseline assessments. Due to the retention of the nylon/titanium cranial anchor base above the skull as a burr hole cover following removal of the infusion system, the specific MRI conditions detailed in the IFU must be taken into account for all post-surgical MRI scans.

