- d. If an MRI of the head is done at screening, the MRI for presurgical planning does not need to be done.
- e. The diagnosis of idiopathic PD will be made before any other screening procedure will take place.
- f. Demographics will include sex, age, race and ethnicity.
- g. Prior and concomitant medications will be recorded from date of informed consent form (ICF) signature till the final study visit on electronic case report form (eCRF). Changes in concomitant medications should be recorded before and after surgery.
- h. Participants will be contacted by telephone on Day 7 or 8 (6 or 7 days after study drug administration) for assessment of AEs.
- i. “Off” state scores will be obtained after at least 12 hours of holding dopaminergic medication.
- j. Participants may take additional levodopa (in addition to their usual dose) if needed to achieve the “on” state.
- k. Prior to the surgery
- l. Vital sign measurements: temperature, heart rate, respiratory rate, and blood pressure will be recorded before surgery, approximately every 30 minutes for at least the first 4 hours after start of infusion (this can be prolonged in 30-minute intervals if the infusion takes longer than 4 hours), and then at approximately 8 and 12 hours after the start of infusion. Of note, the participant may be transferred to an inpatient hospital service for the assessment of vital signs between 4 hours and 12 hours after start of infusion. Height will be measured at screening, whereas weight will be measured at both screening and Week 26 visits.
- m. Coagulation parameters will not be evaluated.
- n. Serum or urine pregnancy tests may be performed, as determined necessary by the Investigator or required by local regulation, to establish the absence of pregnancy at any time during the participation in the study.
- o. Inform the participant that the Hauser Patient Diary should be completed twice per week (on 2 non-sequential days) for 3 consecutive weeks prior to the second screening visit (i.e., the Day -7 to Day -3 visit). After baseline, the participant should complete the Hauser Patient Diary on 2 non-sequential days in the week prior to Day 15, and Week 12, and Week 26.
- p. Assessment only to be performed after the participant has qualified to enroll in the study.
- q. Randomization will occur after all inclusion and exclusion criteria have been met and surgery is scheduled.

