### **3 STUDY DESCRIPTION**

#### **3.1 SUMMARY OF STUDY DESIGN**

This is a Phase 1/2, randomized, double-blind, sham-controlled study designed to assess the safety and tolerability of AAV-GAD administered bilaterally into the STN in participants with Parkinson's disease not adequately controlled with appropriate anti-Parkinsonian medications.

The study will be carried out in the US at approximately 5 sites with established and highly experienced surgical programs for DBS treatment of Parkinson's disease. The principal investigators will be neurosurgeons or neurologists with expertise in the assessment and treatment of participants with Parkinson's disease and with strong backgrounds in clinical research. Each site will also have support personnel knowledgeable in the care of participants with this disorder.

Approximately 14 eligible participants will be randomized to receive 1 of 2 doses of AAV-GAD infused bilaterally into the STN (5 participants per dose group) or sham surgery (bilateral partial-thickness burr hole procedure) (4 participants) and followed for 6 months.

After discussion of the study risks and possible benefits with the Investigator, participants will provide written informed consent and be considered eligible for the study if they satisfy all inclusion and exclusion criteria. Day 1 will be defined as the day of AAV-GAD or sham treatment.

Safety and tolerability of AAV-GAD gene transfer will be assessed by AEs, vital sign measurements, neurological examinations, physical examinations, radiographic imaging of the head (computed tomography [CT] and magnetic resonance imaging [MRI]), clinical laboratory evaluations, electrocardiograms (ECGs), immune response, and the Columbia-Suicide Severity Rating Scale.

A Data and Safety Monitoring Board (DSMB) will be established for this study to provide expert input on safety of the investigational product, surgical procedure, and related issues.

Participants will also be assessed for potential clinical responses of AAV-GAD on Parkinson's disease signs, symptoms, and disabilities using assessments widely used in Parkinson's disease research for evaluating new medications and surgical procedures.

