#### **4.2 EXCLUSION CRITERIA**

1. Women who are pregnant or breastfeeding. Women of childbearing potential are required to have a negative serum pregnancy test at the Screening Visit and within approximately 1 week prior to surgery on Day 1. Participants are considered not of childbearing potential if they are surgically sterile (i.e., they have undergone a hysterectomy or bilateral oophorectomy), or are postmenopausal.
2. Any experimental therapy (drug or biologic) within 3 months prior to Screening.
3. Have a known allergy to any of the non-investigational drugs (e.g., antibiotics and local anesthesia) to be used in the study.
4. Known allergies, hypersensitivity, or intolerance to AAV-GAD excipients.
5. Any prior history of brain surgery for Parkinson's disease.
6. Ongoing treatment with dopamine receptor-blocking drugs.

7. History of any serious cerebral insult, such as head injury, or central nervous system infection, or uncontrolled seizures.
8. Mental retardation or impaired cognitive abilities, as judged by patient history or cognitive impairment as defined by Montreal Cognitive Assessment (MoCA)  $\leq 20$ .
9. Focal or lateralized central nervous system (CNS) neurological deficits other than mild memory disturbance.
10. Neurological features suggestive of the diagnosis of a “Parkinson-plus” disorder (such as progressive supranuclear palsy, multiple system atrophy, corticobasal ganglionic degeneration, or “lower body” Parkinsonism) or normal pressure hydrocephalus.
11. Evidence of lesions or other significant abnormalities on cranial neuroimaging (either CT, MRI, or  $^{18}\text{FDG-PET}$ ) suggesting findings compatible with a probable diagnosis other than Parkinson's disease.
12. Alanine aminotransferase and/or aspartate aminotransferase  $>1.5$  upper limit of normal (ULN) or alkaline phosphatase  $>1.5$  ULN.
13. Clinically relevant abnormality on 12-lead ECG.
14. Administration of any live virus vaccine within 4 weeks of surgery.
15. Evidence of other significant medical or psychiatric disorders, such as psychosis, frequent occurrence of hallucinations, severe depression, significant cognitive decline in recent months, systemic organ failure, or bleeding diathesis, not attributable to adverse effects of anti-Parkinsonian medications.
16. Evidence of active impulse control disorder, or substance or alcohol abuse unrelated to use of dopaminergic medication.

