17. Significant concurrent or recently diagnosed ( $\leq 2$  months prior to the Screening Visit) medical condition that, in the opinion of the Investigator, could affect the participant's ability to tolerate or complete the study.
18. Current immunosuppressive therapy or underlying disorder associated with diminished immunocompetence.
19. Serum platelet count of  $<80,000/\text{mm}^3$ , international normalized ratio (INR)  $>1.3$ , or partial thromboplastin time (PTT)  $>40$  seconds.
20. Score of  $\geq 20$  on the Beck Depression Inventory-II.
21. Acute or chronic systemic and/or local skin infections involving the scalp.
22. Criterion removed in protocol version 6.0.
23. Has any other condition that, at the consideration of the Investigator, makes them inappropriate for entry into the study.
24. Is an employee of MeiraGTx.
25. Is an employee of the Investigator or study site, with direct involvement in the proposed study or other studies under the direction of that Investigator or study site, as well as family members of the employees or the Investigator.

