### **6.2 STUDY PROCEDURES**

The Schedule of Activities (SoA) summarizes the frequency and timing of efficacy, safety, and immunogenicity assessments applicable to this study.

The diagnosis of idiopathic PD will be made before any other screening procedure takes place. During screening, assessments that are not part of the study entry criteria will be performed after the participant has qualified to enroll in the study (as per footnote “p” of the SoA [[Table 1](#)]).

All participants will be provided with an emergency card on enrollment to the study to enable 24-hour contact with study Investigators.

Participants randomly assigned to immediate treatment with AAV-GAD will be scheduled for surgery and complete the full battery of visits through the Week 26 visit (as described in the SoA), and then enter the long-term follow-up MGT-GAD-026 study.

Participants randomly assigned to sham surgery will follow the same visit schedule during the first 6 months, and then enroll in the long-term follow-up MGT-GAD-026 study, in which these participants will be offered treatment with AAV-GAD. The Week 26 visit of this study will serve as the Baseline visit of MGT-GAD-026.

Any medical condition already present at Screening should be recorded as medical history and not be reported as an AE unless the medical condition or signs or symptoms present at screening change in severity, frequency, or seriousness at any time during the study. In such a case, it should be reported as an AE.

The Week 19 visit is a telephone visit for assessment of AEs, changes in control of Parkinsonism, and other neurological events. The following actions must be taken if a participant fails to answer or return phone calls:

- The study-site personnel must attempt to contact the participant to reschedule the missed telephone visit as soon as possible.
- The Investigator or designee must make every reasonable effort to regain contact with the participant (where possible, 3 telephone calls, emails, fax).
- Should the participant continue to be unreachable, they will be considered to have missed the telephone visit.

During visits that include the UPDRS assessment, the MDS-UPDRS Part 3 “off” state assessment should preferably be performed before any other assessments or questionnaires. Site staff are to confirm that the last dose of dopaminergic medication(s) was taken by the participant at least 12 hours before performing the MDS-UPDRS Part 3 “off” state assessment (also see Section 7.2).

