### 7.2 QUESTIONNAIRES AND SCALES

The following assessment tools will be used in this study:

- Columbia Suicide severity rating scale: a measure assessed by the Investigator or a qualified member of her/his team (e.g., a neurologist), used to identify and assess individuals at risk for suicide.
- Beck Depression Inventory-II: a 21-item self-report inventory measuring the severity of depression in adolescents and adults
- Beck Anxiety Inventory: a 21-item self-report inventory measuring the severity of anxiety in adolescents and adults
- Clinical Global Impression-Severity: a 7-point scale completed by the Investigator or a qualified member of her/his team (e.g., a neurologist), to rate the severity of the participant's illness at the time of assessment, relative to her/his baseline state (prior to the surgery)
- Clinical Global Impression-Improvement: a 7-point scale completed by the Investigator or a qualified member of her/his team (e.g., a neurologist) to assess how much the participant's illness has improved or worsened relative to her/his baseline state (prior to the surgery)
- EuroQol-5 Dimensions-5 Levels Survey comprises five dimensions: mobility, self-care, usual activities, pain/discomfort and anxiety/depression. Each dimension has 5 levels: no problems, slight problems, moderate problems, severe problems and extreme problems. The participant is asked to indicate his/her health state by ticking the box next to the most appropriate statement in each of the five dimensions. This decision results in a 1-digit number that expresses the level selected for that dimension. The digits for the five dimensions can be combined into a 5-digit number that describes the patient's health state.

- Montreal Cognitive Assessment: a brief cognitive screening task assessment administered by the Investigator or a qualified member of her/his team (e.g., a neuropsychologist) of different cognitive abilities such as visuospatial skills, executive function, memory, language and attention.
- Parkinson's Disease Questionnaire-39 Scale: a 39-item questionnaire completed by participants that measures health status and quality of life
- Parkinson's Disease Sleep Scale-2: a 15-item scale completed by participants to self-rate and quantify the level of sleep disruption being experienced

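### The baseline Columbia suicide-risk scale is barred until the participant has qualified, and nothing says whether it comes before or after randomization

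*Combined protocol and SAP*

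**What the plan says.** Table 1 lists the "Columbia-Suicide Severity Rating Scale" once before surgery, in the Day -40 to Day -8 screening column, and again at Day 29, Week 12 and Week 26. The screening entry carries footnote p: "Assessment only to be performed after the participant has qualified to enroll in the study". Section 6.2 gives the reason: "assessments that are not part of the study entry criteria will be performed after the participant has qualified to enroll".

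Randomization sits in the same screening column under footnote q: "Randomization will occur after all inclusion and exclusion criteria have been met and surgery is scheduled".

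Section 7.2 describes the Columbia scale as "used to identify and assess individuals at risk for suicide". The Synopsis and Sections 3.1 and 8 list it among the safety measures, and Section 10.1.3.6 plans descriptive summaries by visit.

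No entry criterion in Sections 4.1 or 4.2 names the scale or suicidality. Two exclusions call for a judgment to which the result is relevant. Criterion 15 begins "Evidence of other significant medical or psychiatric disorders, such as psychosis, frequent occurrence of hallucinations, severe depression". Criterion 23 reads "Has any other condition that, at the consideration of the Investigator, makes them inappropriate for entry into the study". Criterion 20 separately excludes a Beck Depression Inventory-II score of 20 or more, and that inventory carries footnote b, so it may be done before qualification.

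**The concern.** The scale is described as a way to find people at risk, yet footnote p allows it only once the entry decision has been made. The Investigator judges psychiatric fitness under criteria 15 and 23 without it. Because its order relative to randomization is open, the result may first be read after a treatment has been assigned.

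Two things are at stake. One is the quality of the judgment that leads to a neurosurgical procedure. The other is the make-up of the analysis sets: someone whose result changes the decision before randomization is a screen failure, whereas the same person found after randomization is a randomized participant who may never be treated. In a trial of about 14, with formal tests planned for MDS-UPDRS Part 3 and GADRP (Section 10.1.1), that difference is visible.

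**Working it through.** The plan gives no figure to reproduce here. The check sets the timing rules side by side and follows one case through the analysis populations.

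**1. Order of scale and randomization.**
- Footnote p: the scale comes after qualification.
- Footnote q: randomization comes after the criteria are met and surgery is scheduled.
- Both fall in the Day -40 to Day -8 column.
- Qualification, scale, randomization satisfies both footnotes. So does qualification, randomization, scale. The text permits either.

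**2. Does the reason in Section 6.2 settle the placement?** Only in part. Fifteen rows of Table 1 carry footnote p. Fourteen of them are cognitive tests, MDS-UPDRS Parts 1, 2 and 4, and other scales that the Synopsis lists as exploratory activity assessments. The Columbia scale is the only listed safety measure among them. Vital signs carry footnote b although no entry criterion names them, so a safety measure without its own criterion is already done alongside the entry assessments.

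**3. Time to surgery.** Section 3.1: "Day 1 will be defined as the day of AAV-GAD or sham treatment". The latest scheduled day for the scale is Day -8.
- Without a Day 0: 7 days from Day -8 to Day -1, plus 1 day to Day 1, gives 8 days.
- With a Day 0: 1 - (-8) = 9 days.

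The result is therefore due at least 8 days before surgery. The interval between scale and randomization cannot be computed, because their order is not given.

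**4. Routes open once a result is known.**
- Before randomization: criteria 15 and 23 can still be applied, since footnote q requires all criteria to be met at that point.
- After randomization, before surgery: Section 4.3 allows discontinuation where a medical condition or circumstance puts the participant at substantial risk, and provides for replacement.

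**5. Effect on the analysis sets.** Section 10.1.2 defines the Intention-to-Treat Population as everyone randomized and the Safety Population as those randomized and treated. Take the planned 5 + 5 + 4 = 14, and suppose one positive baseline result leads to a participant not being treated.

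| When the result is seen | Randomized (ITT) | Treated (Safety) |
|---|---|---|
| Before randomization (screen failure) | 14 | 14 |
| After randomization, participant replaced | 14 + 1 = 15 | 14 |

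In the second row one of 15 Intention-to-Treat members is untreated. Section 6.3 asks for the Week 26 assessments from those who leave after surgery, so this participant may have no outcome data at Week 12 or 26.

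**The case against.** The strongest reply is that the placement is deliberate and internally consistent. Section 6.2 states the rule, the scale is not an entry criterion, and the protocol uses it as an on-study safety measure with descriptive summaries. Mood is also screened before qualification: the Beck Depression Inventory-II has a cut-off under criterion 20, and criterion 15 excludes severe depression and other significant psychiatric disorders. Footnote q's added condition, that surgery be scheduled, leaves room for the scale before randomization.

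Much of this stands. A reader might infer that the Columbia scale is the only structured psychiatric information available, but criterion 20 shows otherwise. A reader might also infer that a finding must end in withdrawal after randomization or in surgery with the finding unweighed. The text does not support that either, because criteria 15 and 23 remain usable up to randomization and Section 4.3 up to surgery.

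The reply does not remove two points. Section 7.2 describes the Beck inventory as a measure of depression severity and the Columbia scale as a measure of suicide risk, so the first does not stand in for the second. And nothing obliges a site to do the scale before randomization. The routes that remain are discretionary, and the available text states no handling of a positive baseline result.

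**Conclusion.** The point holds as a sequencing gap. By rule the baseline Columbia result is unavailable when the participant qualifies, and it may first be seen after randomization. It does not come too late to act on before surgery, given the interval of at least 8 days.

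The statistical cost is one randomized, untreated participant per late finding that stops treatment: 15 in the Intention-to-Treat Population against 14 in the Safety Population for a single case. It would be wrong to read this as a lost treated slot, since Section 4.3 replaces anyone who withdraws before surgery. It would also be wrong to say that every entry decision is affected. Only a positive result not already caught by criteria 15, 20 or 23 could matter, and the documents give no rate for that.

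The size rests on these assumptions: the scale is done within its scheduled window, the late finding leads to non-treatment, and replacement restores 14 treated participants. This is an inexpensive improvement to safety information and to the analysis sets; it does not threaten the trial's validity.

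**What to change.** Reconcile Table 1 footnotes p and q and Section 6.2 with Sections 4.2 and 4.3:

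- Exempt the Columbia scale from footnote p, and word the exception into Section 6.2 so that the two agree.
- State in footnote q that the baseline Columbia result is on file and has been reviewed by the Investigator before eligibility is confirmed and randomization occurs.

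Simply changing the row's footnote from p to b would not be enough. Footnote b expresses only a preferred window (Day -40 to Day -21), sets no order relative to randomization, and would leave Section 6.2 in conflict.

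No threshold and no new exclusion rule is proposed. The Investigator applies the existing criteria with the result in hand. The cost is a few words in the protocol and a short interview in some people who later fail screening. Sample size and analysis methods are unchanged.

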## LIST OF ABBREVIATIONS AND DEFINITION OF TERMS

Abbreviation	Definition
AAV	adeno-associated virus
AAV2	adeno-associated virus serotype 2
AAV-GAD	The investigational product: Two recombinant adeno-associated virus (AAV) serotype 2-glutamic acid decarboxylase (GAD) vectors, GAD65 and GAD67, mixed in a 1:1 ratio (AAV-GAD)
ADL	activities of daily living
ADR	adverse drug/device reaction
AE	adverse event
AR	Adverse Reaction
CI	confidence interval
CMO	Contract Manufacturing Organization
CNS	central nervous system
COVID-19	Coronavirus Disease 2019
CRO	Contract Research Organization
CT	computed tomography
DBS	deep brain stimulation
DKEFS	Delis-Kaplan Executive Function System
DNA	deoxyribonucleic acid
DSMB	Data and Safety Monitoring Board
ECG	Electrocardiogram
eCRF	electronic case report form
EDC	electronic data capture
EW	early withdrawal
FDA	Food and Drug Administration
FDG	 fluorodeoxyglucose
GABA	gamma-aminobutyric acid
GAD	glutamic acid decarboxylase
GADRP	glutamic acid decarboxylase-related pattern
GCP	Good Clinical Practice
GPi	globus pallidus internal segment
HVLT-R	Revised Hopkins Verbal Learning Test
IB	Investigator's Brochure
ICF	informed consent form
ICH	International Council for Harmonisation
IFU	Instructions for Use
IND	Investigational New Drug

Abbreviation	Definition
INR	international normalized ratio
IRB/IEC	institutional review board/independent ethics committee
ITT	Intention-to-Treat
MedDRA	Medical Dictionary for Regulatory Activities
MMRM	mixed model for repeated measures
MoCA	Montreal Cognitive Assessment
MP	Monitoring Plan
MPTP	1-methyl-4-phenyl-1,2,3,6-tetrahydropyridine
MRI	magnetic resonance imaging
MSA	multiple system atrophy
NCI CTCAE	National Cancer Institute Common Terminology Criteria for Adverse Events
NHP	nonhuman primate
NOAEL	No Observed Adverse Effect Level
PDRP	Parkinson's disease-related pattern
PET	positron emission tomography
PSP	progressive supranuclear palsy
PTT	partial thromboplastin time
RSI	Reference Safety Information
SAE	serious adverse event
SAP	Statistical Analysis Plan
SAR	serious adverse reaction (device or drug)
SNpc	substantia nigra pars compacta
SNr	substantia nigra pars reticulata
SoA	Schedule of Activities
STN	subthalamic nuclei(us)
SUSAR	suspected unexpected serious adverse reaction
TMT	Trail Making Test
UK	United Kingdom
ULN	upper limit of normal
UPDRS	Unified Parkinson's Disease Rating Scale
MDS-UPDRS	Movement Disorder Society-Sponsored Revision of the UPDRS
US	United States
UV	Unscheduled visit
WOCBP	women of childbearing potential

